3.3.3 Exclusion Criteria for Investigators

Investigator must not be or must not have been an employee of AstraZeneca or participated as an investigator in the Seroquel XR clinical program for MDD.

4. STUDY CONDUCT

4.1 Questionnaire Validation Plan

In order to effectively evaluate the drug utilisation questionnaire prior to implementation, questionnaire validation will be implemented with a sample of psychiatrists and pilot testing of the questionnaire will be performed. Face validity assessment and pilot testing will be done in a single language.

4.1.1 Face Validity

Prior to administering the questionnaire, an evaluation by two practicing psychiatrists will be performed. The purpose of this evaluation will be to determine whether there are any items that are not readily understood or where the response requested may be misinterpreted. Face validity will be assumed if $\leq 5\%$ of items on the questionnaire are flagged as problematic by both psychiatrists.

4.1.2 Pilot Testing

Pilot testing of the questionnaire is intended to test the instrument's utility and the methods employed for abstraction of data in different practice settings. Pilot testing of the questionnaire will be conducted in multiple sites that are representative of practice settings. The pilot testing will be performed using different sites/investigators than those participating in this study. Sites included in pilot testing are contacted on a separate time schedule than those in this study to ensure that any modifications required are completed and tested prior to the start of this study.

The pilot testing will consist of the completion of the questionnaire for up to 20 patients. In conjunction with the local Ethics Committee the requirements for collection of Informed Consent during the pilot testing of the questionnaire will be determined.

AstraZeneca may update the drug utilization questionnaires based on pilot study results and recommendation of the Scientific Advisory Board.

4.1.3 Translation of the drug utilisation questionnaire

Translation will be done after the validation of the questionnaire. All translations to the respective languages will be done using forward and backward translations.

4.2 Questionnaire Administration

4.2.1 Timeline for questionnaire administration

The exact index date for each country will be selected to optimise preparations leading to completion of drug utilisation questionnaires at all sites within a country following Good Pharmacoepidemiology Practices (PDS 2008).

Contact with investigators and site preparatory activities are initiated following the index date, which will correspond to a date approximately 12 months following the launch of Seroquel XR for MDD in each country.

Preparatory activities for completion of the drug utilisation questionnaires at each site will rely on automated and manual review of data from patient medical records in order to identify patients meeting study inclusion criteria. This selection includes consideration of the inception cohort definition (i.e., initiation of treatment with Seroquel XR in the time interval 3 months after launch up to the index date).

Once site preparatory activities are concluded, including the obtaining of informed consent from the patient, data abstraction of patient medical records using the drug utilisation questionnaire will begin.

Information on the Physician questionnaire related to physician characteristics will be completed based upon the best available recollection by the investigator. Patient questionnaire data will be abstracted from the medical records of the patients maintained at the official location for storage of records for the site/investigator and will be performed by a representative of AstraZeneca.

4.2.2 Key Variables - Psychiatrists, Subjects, and Drug Utilisation

The drug utilisation questionnaire is constructed to collect key variables on characteristics of physicians, patients and the drugs utilised in the medical management of depressive episodes in MDD where the treatment regimen includes Seroquel XR.

Information on participating psychiatrists will include:

- location of practice (i.e., country, region, and city or town)
- age
- gender
- years in practice
- practice setting (i.e., mental health clinic, university-affiliated hospital, community hospital, private practice office, other)
- proportion of patient volume in hospital versus non-hospital

- approximate proportion of patients with a diagnosis of MDD in their practice

Information on patients will include:

- demographics (date of birth, gender, race)
- source and reason for referral of the patient
- general medical and psychiatric history (i.e., date of first depressive episode, start date of most recent depressive episode, month and year of diagnosis of MDD, total number of depressive episodes over lifetime, number of depressive episodes during the 12 months up to the latest consultation, presence of psychotic symptoms in the past, psychiatric co-morbidities (anxiety disorders, substance use, other Axis I, or other Axis II disorder), other medical co-morbidities (i.e., hypertension, obesity, diabetes, other cardiovascular), ever been hospitalised for a psychiatric condition, ever hospitalised for MDD, and whether hospitalised during most recent depressive episode)

Information on drug utilisation will include, where recorded:

- treatment history including details on current and past drug treatments for MDD (including Seroquel XR) within the past 12 months (historical information based on patient reported drug use may be required if physician has been treating the patient for < 12 months), dose/duration of drugs used to treat MDD (including any drug treatments for MDD noted in the patient's medical record that were prescribed by other physicians), including changes in medication, date of initiation/end for each drug; and whether drug treatments for MDD prescribed with Seroquel XR were still prescribed on the index date; for Seroquel XR treatment details include frequency of prescriptions by dose, prescribed days supply by dose, initial dose, usual (modal) dose, maximum dose
- diagnosis for which Seroquel XR is being prescribed
- number of visits to the psychiatrist during the timeframe that Seroquel XR has been prescribed
- Presence of psychotic symptoms at time of prescription of Seroquel XR
- Clinical Global Impression of the patient prior to initiation of Seroquel XR

Data will be collected either via a paper questionnaire for completion by the treating psychiatrist, or be extracted from medical records or related records by AstraZeneca representative using an electronic Case Report Form (eCRF).

The Questionnaire designed for collecting Physician and Patient-level data are provided in [Appendix B](#). The Patient-level questionnaire may be revised based upon the findings of the pilot study and the recommendations of the Scientific Advisory Board.

4.3 Role of scientific advisory board

A board comprised of independent, external psychiatrists from each of the participating EU countries will provide scientific support to AstraZeneca.

The scope of the services will include:

- Provide scientific advice regarding the protocol and conduct of the study
- Ensure that the selected population included in the study are representative of the distribution in each country

5. SAMPLE SIZE AND PRECISION

Data will be collected from a total of 100-400 patients per country. As a questionnaire will be used to collect the data, the precision around responses is further discussed.

The proportion of patients prescribed a specified daily dose of Seroquel XR is of particular interest. The [PHARMO Report](#) (Institute for Drug Outcomes Research) Part 1 described the distribution of doses of Seroquel XR prescribed to individuals in the Netherlands. The proportion of patients taking Seroquel XR at various dose levels varied from 1% to 67%. The 95% confidence interval for the estimate of a proportion can be calculated for a general situation (i.e., and as applied in this study, the proportion of patients receiving a given dose of Seroquel XR in the sample from each country); for sample sizes of 100, 200, 300 and 400 is provided in [Table 2](#).

Sample sizes of 100-400 patients will provide reasonable precision for a wide range of the estimated proportions of patients receiving a given dose of Seroquel XR in a given country.

Table 2 Precision of Estimated Proportions for a Sample Size of 100 to 400 (2-sided 95% Confidence Intervals)

Estimated Proportion	Sample size = 100	Sample size = 200	Sample size = 300	Sample size = 400
6%	(1.3%,10.7%)	(2.7%,9.3%)	(3.3%,8.7%)	(3.7%,8.3%)
11%	(4.9%,17.1%)	(6.7%,15.3%)	(7.5%,14.5%)	(7.9%,14.1%)
16%	(8.8%,23.2%)	(10.9%,21.1%)	(11.9%,20.1%)	(12.4%,19.6%)
21%	(13%,29%)	(15.4%,26.6%)	(16.4%,25.6%)	(17%,25%)
26%	(17.4%,34.6%)	(19.9%,32.1%)	(21%,31%)	(21.7%,30.3%)

31%	(21.9%,40.1%)	(24.6%,37.4%)	(25.8%,36.2%)	(26.5%,35.5%)
36%	(26.6%,45.4%)	(29.3%,42.7%)	(30.6%,41.4%)	(31.3%,40.7%)
41%	(31.4%,50.6%)	(34.2%,47.8%)	(35.4%,46.6%)	(36.2%,45.8%)
46%	(36.2%,55.8%)	(39.1%,52.9%)	(40.4%,51.6%)	(41.1%,50.9%)
51%	(41.2%,60.8%)	(44.1%,57.9%)	(45.3%,56.7%)	(46.1%,55.9%)
56%	(46.3%,65.7%)	(49.1%,62.9%)	(50.4%,61.6%)	(51.1%,60.9%)
61%	(51.4%,70.6%)	(54.2%,67.8%)	(55.5%,66.5%)	(56.2%,65.8%)
66%	(56.7%,75.3%)	(59.4%,72.6%)	(60.6%,71.4%)	(61.4%,70.6%)
71%	(62.1%,79.9%)	(64.7%,77.3%)	(65.9%,76.1%)	(66.6%,75.4%)
76%	(67.6%,84.4%)	(70.1%,81.9%)	(71.2%,80.8%)	(71.8%,80.2%)
81%	(73.3%,88.7%)	(75.6%,86.4%)	(76.6%,85.4%)	(77.2%,84.8%)

5.1 Measures to Minimize Bias

A number of measures will be implemented to ensure the completion of the drug utilisation questionnaire is conducted in a systematic, professional, and unbiased manner:

- The drug utilisation questionnaire will be evaluated through pilot testing of the questionnaire with medical records of psychiatrists treating MDD patients to ensure that questions are understood, and not ambiguous or misleading
- Programming of the Electronic Data Capture version of the questionnaire (eCRF) will be reviewed by a quality control process and simulation prior to implementing the questionnaire
- Standard scripts will provide consistent instruction on completion of the questionnaire
- All individuals performing abstraction of data from medical records will be trained on appropriate data abstraction techniques
- Physicians who participated as an investigator for the Seroquel XR clinical development program for MDD will not be eligible to participate

6. ETHICAL AND REGULATORY REQUIREMENTS

6.1 Ethical conduct of the study

The Study will be performed in accordance with ethical principles that are consistent with the Declaration of Helsinki, ICH GCPs and the applicable legislation on Non-Interventional Studies.

The Investigator will perform the study in accordance with the regulations and guidelines governing medical practice and ethics in the country and in accordance with currently acceptable techniques and know-how.

6.1.1 Ethics review

The final protocol of the Study, including the final version of the Subject Informed Consent Form, must be approved or given a favourable opinion in writing by the Ethics Committee.

The Ethics Committee must also approve any amendment to the protocol, according to local regulations.

6.2 Subject data protection

The Subject Informed Consent Form will incorporate wording that complies with relevant data protection and privacy legislation. Pursuant to this wording, subjects will authorise the collection, use and disclosure of their personal data by the Investigator and by those persons who need that information for the purposes of the study.

The Subject Informed Consent Form will explain that study data will be stored in a computer database, maintaining confidentiality in accordance with the local law for Data Protection.

The Subject Informed Consent Form will also explain that a monitor of AZ or a monitor of company representing AZ, will require direct access to the signed subject informed consent forms. The Subject Informed Consent Form will explain that for data verification purposes, monitor will require direct access to source documents that are part of the hospital or practice records relevant to the Study.

6.3 Informed consent

Principal Investigator(s) at each site will:

- Ensure each patient is given full and adequate oral and written information about the nature, purpose, possible risk and benefit of the study
- Ensure each patient is notified that they are free to discontinue from the study at any time
- Ensure each patient is given the opportunity to ask questions and allowed time to consider the information provided
- Ensure each patient provides signed and dated informed consent before collecting any data from the patient's record
- Ensure the original, signed Informed Consent Form(s) is/are stored in the Investigator's Study File
- Ensure a copy of the signed Informed Consent Form is given to the subject

- Ensure that the provision of anything of value to the patients who participate in the study as well as any provisions for subjects harmed as a consequence of study participation are described in the informed consent form that is approved by an Ethics Committee

6.4 Changes to the protocol and informed consent form

If there are any substantial changes to the study protocol, then these changes will be documented in a study protocol amendment and where required in a new version of the study protocol.

The amendment should be approved by each Ethics Committee and if applicable, also the national regulatory authority, before implementation. Local requirements should be followed for revised protocols.

AstraZeneca will distribute any subsequent amendments and new versions of the protocol to each Principal Investigator.

If a protocol amendment requires a change to a site's Informed Consent Form, AstraZeneca and the site's Ethics Committee should approve the revised Informed Consent Form before the revised form is used.

If local regulations require, any administrative change will be communicated to or approved by each Ethics Committee.

6.5 Audits and inspections

Authorized representatives of AstraZeneca, a regulatory authority, or an Ethics Committee may perform audits or inspections at the site, including source data verification. The purpose of an audit or inspection is to systematically and independently examine all study-related activities and documents, to determine whether these activities were conducted, and data were recorded, analysed, and accurately reported according to the protocol, GCP, guidelines of the ICH, and any applicable regulatory requirements. The investigator will contact AstraZeneca immediately if contacted by a regulatory agency about an inspection at the site.

7. STUDY MANAGEMENT BY ASTRAZENECA

7.1 Pre-study activities

Before the first patient is selected for the study and retrospective data are abstracted, it is necessary for a representative of AstraZeneca to visit the investigational study site to:

- Determine the nature of the medical records storage retrieval
- Determine availability of appropriate patients for the study

- Discuss with the investigator(s) (and other personnel involved with the study) their responsibilities with regard to protocol adherence, and the responsibilities of AstraZeneca or its representatives.

7.2 Training of study site personnel

Before the first patient is entered into the cohort, an AstraZeneca representative will review and discuss the requirements of the protocol and related documents with the investigational staff and also train them in any specific procedures.

The Principal Investigator will ensure that appropriate training relevant to the study is given to all of these staff, and that any new information relevant to the performance of this study is forwarded to the staff involved.

The Principal Investigator will maintain a record of all individuals involved in the study.

7.3 Monitoring of the study

During the study, an AstraZeneca representative will have regular contacts with the study site including visits to:

- Provide information and support to the investigator(s)
- Confirm that the investigational team is adhering to the protocol, that data are being accurately collected and recorded in the physician part of the questionnaire
- Ensure that the subject informed consent forms are signed and stored at the investigator site
- Extract patient data from subject's medical records or other records relevant to the study, using questionnaire in the eCRF. This will require direct access to all original records for each subject (i.e., clinic charts)
- Perform source data verification (a comparison of the data in the questionnaire with the subject's medical records at the hospital or practice, and other records relevant to the study). This will require direct access to all original records for each subject (i.e., clinic charts).

The AstraZeneca representative will be available between visits if the investigator or other staff at the site need information and advice about the study conduct.

8. DATA MANAGEMENT

8.1 Collection, monitoring, processing of data and archiving

The investigator will complete the physician part of the drug utilisation paper questionnaire. The monitor will visit the site to extract data from the completed physician questionnaires.

The monitor will have direct access to medical records and other related information for consented study patients. Patient drug utilization data will be entered in the study eCRF by the monitor at the Investigator's site.

Data entered in the eCRF system will be immediately saved to a central database and changes tracked to provide an audit trail. When data have been entered reviewed and edited, data will be locked to prevent further editing. A copy of the e-CRF will be archived at the Investigator's site.

The data will be manually reviewed and queries raised as appropriate to correct inconsistencies or errors. Medical history and medications will be coded using relevant dictionaries.

8.2 Reporting and publication of data

AstraZeneca is obliged to analyse and report all study data as described in the protocol.

In accordance with the Declaration of Helsinki, both authors and publishers have ethical obligations. In publication of the results of the study, the authors are obliged to preserve the accuracy of the results. Negative as well as positive results should be published or otherwise publicly available. AstraZeneca endeavours to publish the results of study and is committed to ensure that the data are reported in a responsible and coherent manner.

9. ANALYSIS

Data obtained from the drug utilisation questionnaire will be reported descriptively. No statistical comparison will be conducted. Summary statistics will be provided. There will be no imputation for any missing values. For continuous variables, the number of responses, mean, median, minimum, maximum, and standard deviation will be provided. For discrete variables, the number of responses and proportion represented by each category will be summarized. Prescribing practices and drug utilisation data will be reported by country permitting comparisons across countries.

9.1 Participating psychiatrists data

Number of participating psychiatrists, and their age, gender, years in practice, practice setting, psychiatric patient volume, approximate proportion of patients with a diagnosis of MDD in their practice will be summarized descriptively by country and overall.

9.2 Patient's demographic data and psychiatric history

Summary statistics will be provided by country and overall for patient's demographics data including age, gender, and race, and for patient's medical history including years since first depressive episode, year of MDD diagnosis, number of depressed episodes over lifetime, number of depressive episodes during the 12 months up to the latest consultation, presence of psychotic symptoms in the past, presence of psychotic symptoms at start of Seroquel XR

treatment, psychiatric co-morbidities (anxiety disorders, substance use, other Axis I, or other Axis II disorder), other medical co-morbidity (hypertension, obesity, diabetes, other cardiovascular disorder), ever been hospitalised for a psychiatric condition), as well as for the number of visits to the psychiatrist during the timeframe that Seroquel XR has been prescribed.

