2.1 Overall study design

This is a multinational, multicenter, retrospective, observational study of antidepressant drug utilisation among an inception cohort of patients under specialists (psychiatrists) care who are prescribed Seroquel XR for treatment of major depressive episodes associated with MDD following launch of the indication in each country. The study will be conducted in 5 European countries: Germany, Italy, Romania, Spain, and Sweden to ensure geographic representation across European member states. The sponsor may include alternate EU country(ies) based upon limited use of Seroquel XR for MDD in the countries listed and whose selection will maintain geographic representation among EU countries.

The inception cohort is defined as patients initiating Seroquel XR (as add-on therapy or as monotherapy) during a 9 month period corresponding to 3 to 12 months following the launch of the product in each country for the MDD indication. In the period immediately after launch, physicians may not be aware of the approval of Seroquel XR for add-on treatment for MDD. Therefore, patients treated with Seroquel XR within the 3 months after launch will not be included in the inception cohort because they are not likely to be representative of patients

[figure not shown]
treated in subsequent periods. A drug utilisation questionnaire will be used to collect study data. Data collection will be initiated following a study-defined index date, approximately 12 months after product launch. All study sites within a country will be assigned the same index date and will not be contacted prior to the index date.* Initiation of site-specific activities for selection of patient records meeting study selection criteria will commence on or following the index date. Data on drug utilisation will be censored on the index date. This approach will ensure that study procedures do not influence prescribing practices.

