3.3.1 Inclusion Criteria for Patients

1. Provision of informed consent before initiation of any collection of questionnaire data.
2. Female and male aged 18 years and over.
3. Documented clinical diagnosis of Major Depressive Disorder, Single Episode, or Recurrent.
4. Initiation of Seroquel XR for treatment of MDD during the period defining the inception cohort, i.e. from 3 months after launch until the index date.

The prescription of the medicinal product is clearly separated from the decision to include the patients in the study.

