(1) Specific drug name (generic or brand names)	(2) Start date (day/mth/year) Check for “on demand” or prn use)	(3) End Date (day/mth/year)	(4) Dose (specify Unit)	(5) Did the dose change at initiation of Seroquel XR?	(6) Most recent dose prior to [INDEX DATE] (if different than at initiation)	(7) Date of most recent dose change (day/mth/year)
	___/___/___  prn	___/___/___  Still prescribed at [INDEX DATE]	_____	 Increase  Decrease  Remained the same  Not applicable	_____  Not applicable	___/___/___  Not applicable
	___/___/___  prn	___/___/___  Still prescribed at [INDEX DATE]	_____	 Increase  Decrease  Remained the same  Not applicable	_____  Not applicable	___/___/___  Not applicable
	___/___/___  prn	___/___/___  Still prescribed at [INDEX DATE]	_____	 Increase  Decrease  Remained the same  Not applicable	_____  Not applicable	___/___/___  Not applicable
	___/___/___  prn	___/___/___  Still prescribed at [INDEX DATE]	_____	 Increase  Decrease  Remained the same  Not applicable	_____  Not applicable	___/___/___  Not applicable

Seroquel XR Treatment

Was the patient experiencing psychotic symptoms at initiation of Seroquel XR?

- Yes
- No
- Unknown

Which disorder was Seroquel XR prescribed for?

Please select all that apply

- MDD
- Schizophrenia
- Bipolar disorder
- Other – please specify _____

How many times has the investigator seen this patient since initiation of Seroquel XR?

__ visits

What is your estimate of patient adherence to the prescribed treatment regimen that included Seroquel XR for depression?

___ % of time adherent to prescribed dose(s) (range: 0 – 100%)

(Investigator assessment)

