		None	Did not significantly interfere with Subject's functioning	Significantly interfered with Subject's functioning	Outweighed therapeutic effect (Not tolerable, Needed to stop medication)
Therapeutic effect	Marked vast improvement. Complete or nearly complete remission of all symptoms				
	Moderate improvement. Partial remission of symptoms				
	Minimal slight improvement				
	Unchanged or worse				

Unknown or Not assessed
(Investigator assessment)

When was the last consultation date for this patient?

__ / __ / ____
day / mo / year

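### The Appendix B visit item counts visits since Seroquel XR initiation with no end point, while Sections 4.2.2 and 9.2 define visits during the time it was prescribed

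*Protocol*

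**What the plan says.** Protocol Section 4.2.2 lists visits among the drug utilisation variables, and Section 9.2 summarises them by country and overall in the same words: the "number of visits to the psychiatrist during the timeframe that Seroquel XR has been prescribed". The window is therefore the time on prescription.

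The Appendix B item, under Seroquel XR Treatment, reads: "How many times has the investigator seen this patient since initiation of Seroquel XR". It names a start but no end.

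Section 2.1 states: "Data on drug utilisation will be censored on the index date". It also states that "All study sites within a country will be assigned the same index date", and that sites are not contacted before that date. Abstraction therefore always comes after the index date.

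Patients enter the cohort by starting Seroquel XR "during a 9 month period corresponding to 3 to 12 months following the launch of the product in each country". Section 3.3.1 gives the same window, ending at the index date.

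Elsewhere the form allows for stopping. The concurrent-drug table has start and end dates and a box beginning "Still prescribed at" the index date. It also asks "When was the last consultation date for this patient". It does not ask for the dates of individual visits.

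**The concern.** The defined variable and the collected variable have different windows.

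- **Patients who stopped before the index date:** the form's count includes visits made off the drug.
- **All patients, including those still on treatment:** as worded, the item can also take in visits between the index date and the day of abstraction. Other items in Appendix B carry an explicit index-date limit, but this one does not.
- **Who was visited:** the definition refers to the psychiatrist and the form to the investigator. These may be the same person, but the documents do not say so.

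What is at stake is whether the 9.2 summary means what it says. Describing differences in treatment practice between countries is a study objective (Section 1.1), and Section 9 expects the by-country reports to be read against each other. A figure labelled as on-treatment visits, but collected over a longer and unbounded window, would mislead most where many patients stopped or abstraction came late.

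A weaker concern is that Section 9.2 names only a count, although time from initiation to the index date differs widely between patients by design.

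**Working it through.** The protocol gives no figure for visits, visit rate, uptake over time or stopping, so there is no plan figure to reproduce. The windows come from the protocol. The rates below are assumptions chosen only to show size.

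**1. The windows compared**

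| Source | Start | End |
|---|---|---|
| Sections 4.2.2 and 9.2 | initiation | end of prescription |
| Section 2.1 censoring rule | – | index date |
| Appendix B item | initiation | none stated |

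Read together, the first two rows end at the earlier of the end date and the index date. The form's window is longer for anyone who stopped, and for anyone seen between the index date and abstraction.

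**2. Can it be corrected later?**

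The form holds one total, the Seroquel XR dates and one last consultation date. If that last date falls on or before both the end date and the index date, the total is unaffected. If it falls later, at least one visit lies outside the window, but the number is unknown. Affected patients can be flagged, but their counts cannot be corrected.

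**3. Size of the overstatement to the index date**

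Assumptions: 1 visit per month, on or off the drug; starts spread evenly over the 9 months; a fraction *q* of patients has a stopping time uniform on 0-3 months, capped at the index date.

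- Mean time since initiation: 9/2 = 4.5 months, so 4.5 visits on the form.
- Mean time on drug in the stopping group: ∫₀³ (1 − t/3)(1 − t/9) dt = 3 − 2 + 1/3 = 1.33 months.
- Ratio in that group: 4.5/1.33 = 3.4.
- *q* = 0.2: 0.8 × 4.5 + 0.2 × 1.33 = 3.87 months on drug; 4.5/3.87 = 1.16, an overstatement of 16%.
- *q* = 0.4: 0.6 × 4.5 + 0.4 × 1.33 = 3.23 months on drug; 4.5/3.23 = 1.39, an overstatement of 39%.

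**4. Visits after the index date**

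Here a different stopping assumption is used: 30% stop at a uniformly distributed point of their follow-up. The on-drug mean is 0.7 × 4.5 + 0.3 × 2.25 = 3.8 visits. If abstraction comes 3 or 6 months after the index date and those visits are counted, the form gives 4.5 + 3 = 7.5 or 4.5 + 6 = 10.5.

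**5. Count and follow-up length**

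Keep 1 visit per month and let the start-date density vary over the 9 months.

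| Uptake | Mean start (months into window) | Mean time to index date (months) | Mean count | Visits per month |
|---|---|---|---|---|
| Rising linearly | 6 | 9 − 6 = 3 | 3.0 | 1.0 |
| Even | 4.5 | 4.5 | 4.5 | 1.0 |
| Falling linearly | 3 | 9 − 3 = 6 | 6.0 | 1.0 |

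The mean count doubles from the first row to the last with no difference in visit frequency.

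**6. Why a rate alone does not repair the form**

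Dividing the since-initiation count by on-drug months gives 4.5/3.87 = 1.16 or 4.5/3.23 = 1.39 visits per month, against a true 1.0. The numerator must be right first.

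**The case against.** The strongest reply has four parts.

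- **A rate belongs to the SAP.** The SAP is not shown, the protocol calls the variable a count, and the dates needed for a denominator are collected. This stands against the person-time point, which is therefore only secondary. It does not answer the form mismatch, because no analysis plan can date undated visits.
- **Section 2.1 already sets an end.** Visits are listed under drug utilisation, so the index-date censoring rule covers them. That is fair as a rule, but the person abstracting works from the form, where the rule is not repeated. It also says nothing about visits between stopping and the index date.
- **The form is not final.** Sections 4.1.2 and 4.2.2 allow revision after the pilot and on advisory board advice. This makes the correction easy but does not make it for the sponsor.
- **The sizes are assumed.** This is correct. The 3.0 and 6.0 counts need uptake that rises from, or falls to, zero, and the 3.4-fold ratio needs all stopping to be early with attendance unchanged.

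A reader might infer two stronger things. One is that the count does not reflect visit frequency at all. It does, because a count is rate times time: with even uptake, rates of 0.5, 1 and 2 per month give 2.25, 4.5 and 9.0 visits to the index date. The other is that stopping makes the collected country counts differ. If stoppers keep attending at the same rate, the since-initiation count to the index date stays at 4.5 whether 0%, 30% or 60% stop. It is the variable as defined that falls with stopping, and the form misses that fall.

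**Conclusion.** The form and the definition contradict each other, and the passages must be reconciled. Followed as written, the form gives too high an on-treatment count for any patient who was seen after stopping, and it can do so for any patient seen between the index date and abstraction. The data collected do not allow correction afterwards.

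The size is illustrative: 16-39% overall if 20-40% stop within 3 months and keep attending at the same rate, and more if post-index visits are counted. All of these rates are assumptions. If nobody stopped and no post-index visits were counted, the error would be zero.

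The raw count also mixes visit frequency with follow-up length. That makes country means harder to read but is not an error in the protocol.

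The consequence is limited to one descriptive variable. Section 9 plans no statistical comparison, and the precision figures in Section 5 concern dose proportions and are untouched.

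**What to change.** 1. Reword the Appendix B item to count visits from Seroquel XR initiation to the earlier of the Seroquel XR end date and the index date. Because each dose change has its own line, say that the end date is that of the last Seroquel XR line. State whether only visits to the investigator count, and use the same term in Sections 4.2.2 and 9.2.
2. In Section 9.2 or the SAP, add by country the visits per patient-month on Seroquel XR: total visits divided by total months over the same window, from the start and end dates already collected. Keep the raw count beside it.

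The first change costs one line of a form that is still open to revision, and is cheapest before translation and eCRF programming. The second costs one derived summary and no new data.
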